4.1. Planned Analyses

A primary endpoint analysis to assess sample size re-estimation was planned to be conducted at the interim time point, when 50% of the 100 planned participants have been followed for 26 weeks from randomization or withdrawn from the initial 26 weeks of the study and have been assessed for the primary endpoint. The primary analysis was planned to be conducted after all participants complete Week 26 or withdraw from the study prior to Week 26. Analyses will be performed on data for the 26-week randomized Treatment Period. The final study analysis was planned to be conducted at the end of the study.

Due to the early termination of the study, the planned interim analysis for sample size re-estimation and the planned primary analysis will not be conducted, and the final study analysis will be performed after the last participant in the study has completed the 26-week Treatment Period.

4.2. Changes from Analyses Specified in the Protocol

As mentioned in Section 4.1, the planned interim analysis for sample size re-estimation and the planned primary analysis as specified in Protocol Amendment 2 (PA2) will not be conducted due to the termination of the study. Only the final study analysis after the last participant in the study has completed the 26-week Treatment Period will be performed.

In addition, no hypothesis testing or inferential statistics for the purpose of treatment comparisons will be performed due to the reduction in sample size because of few participants enrolled. Estimands defined in PA2 are no longer applicable and, thus, are removed from the SAP.

SAP Version	Version Date	Change	Rationale
1.0	29 Jun 2021	Not applicable	Original version
2.0	DD MMM 2022	 Changes to align with PA2: Added additional secondary endpoints: Loss of TMA response Changes from Baseline in hematologic parameters at all scheduled visits Increases in hemoglobin ≥ 1 g/dL at Week 26 Elevated "change in patient-reported outcomes as measured by FACIT-Fatigue" to the secondary endpoint Added an exploratory endpoint to assess overall survival Added the Modified Intent-to-Treat Set as the primary analysis set; removed the Enrolled Set Updated the Per-Protocol Set definition to reflect the revised inclusion/exclusion criteria Changes from analyses specified in PA2: Removed the interim analysis for sample size re-estimation and the primary analysis Removed descriptions on estimands corresponding to the primary and key secondary endpoints Combined key secondary endpoints and additional secondary endpoints will be summarized in descriptive statistics 	To reflect changes made in PA2 and in the planned analyses due to the early termination of the study

4.3. Changes from Analyses Specified in the Previous Version of the SAP

Abbreviations: FACIT = Functional Assessment of Chronic Illness Therapy; PA2 = Protocol Amendment 2; SAP = statistical analysis plan; TMA = thrombotic microangiopathy

5. **DEFINITIONS**

5.1. **Primary Endpoint**

The primary efficacy endpoint of the study is complete TMA response during the 26-week randomized Treatment Period.

Complete TMA response is defined as normalization of hematologic parameters (platelet count and LDH) and \geq 30% improvement in estimated glomerular filtration rate (eGFR) from Baseline (Table 2).

Table 2:	Overview of Complete Thromb	ootic Microangiopathy Response
----------	------------------------------------	--------------------------------

		TMA Response Parameter
Complete TMA response	Hematologic response	 Normalization of platelet count (defined as platelet count ≥ 150000/µL) without transfusion support during the prior 7 days Normalization of LDH (defined as LDH
		\leq 1.5 × upper limit of normal)
	Renal response	• Improvement in eGFR of ≥ 30% compared to Baseline

Abbreviations: eGFR = estimated glomerular filtration rate; LDH = lactate dehydrogenase; TMA = thrombotic microangiopathy

If a participant is not on dialysis at Baseline, baseline eGFR will be defined as the last nonmissing assessment value prior to the start of study treatment. If a participant is on dialysis at Day 1, baseline eGFR will be set to 10 mL/min/1.73 m². If a participant is on dialysis during the entire 26-week randomized Treatment Period or through early discontinuation of study drug, then the change in eGFR will not be calculated.

For complete TMA response, participants must have met all 3 TMA response parameters simultaneously, with each component meeting the requirement at 2 separate assessments obtained at least 24 hours apart, and any measurement in between. The first laboratory value will be assessed based on central laboratory results; the second laboratory value will be assessed based on the earliest value obtained \geq 24 hours after the first value and may be based on central or local laboratory results.

Participants will be classified as nonresponders if they do not have any TMA response observed before the following intercurrent events: treatment discontinuation or start of disallowed therapy or medicine, regardless of whether the TMA response is observed after these intercurrent events. For other participants without the above intercurrent events, whether the TMA response occurs by 26 weeks will be assessed using all available assessments within the 26-week randomized Treatment Period.

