## 3.2. Definitions of Endpoints

### 3.2.1. Complete TMA Response

Complete TMA Response is defined as the normalization of hematologic parameters (platelet count and LDH) and  $\geq 30\%$  improvement in estimated glomerular filtration rate (eGFR) from baseline (Table 5).

For Complete TMA Response, participants must have met all 3 TMA response parameters, with each parameter meeting the requirement at 2 separate assessments obtained at least 24 hours apart, and any measurement in between. The first laboratory value will be assessed based on central laboratory results; the second laboratory value will be assessed based on the earliest value obtained  $\geq 24$  hours after the first value and may be based on central or local laboratory results.

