#### Disease Characteristics

4. TMA within  $\leq$  14 days prior to Screening is associated with at least 1 of the following triggers:
  - a. Autoimmune (lupus nephritis, systemic sclerosis associated TMA [SSc-TMA])
  - b. Infection
  - c. Solid organ transplant (eg, kidney, pancreas, liver, heart, small bowel)
  - d. Drugs
  - e. Malignant hypertension

5. Confirmation of all of the following laboratory findings during the Screening Period and/or  $\leq 14$  days prior to the start of the Screening Period:
  - a. Platelet count  $< 150,000/\mu\text{L}$
  - b. Lactate dehydrogenase  $\geq 1.5 \times \text{ULN}$  and hemoglobin  $\leq \text{LLN}$  (based on age and sex)
  - c. Acute kidney injury as defined by meeting 1 or more of the following criteria (for kidney transplant recipients, the pre-TMA value is based on post-transplant eGFR):
    - Acute decline in eGFR  $\geq 50\%$  from pre-TMA value (pre-TMA value must be  $\leq 12$  months prior to Screening)
    - New acute kidney injury with an eGFR  $\leq 30 \text{ mL/min}/1.73 \text{ m}^2$
    - New initiation of dialysis due to TMA requiring  $> 1$  session and for no more than 14 days prior to Screening

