6.3. Per-Protocol Set

The Per-Protocol Set (PPS) will consist of mITT participants who met all of the following criteria. The primary analysis will be repeated on the PPS as supplementary analyses. PPS will be analyzed according to the participants' randomized treatment assignment.

- 1. Participants who received full randomized intervention during the 26-week randomized Treatment Period
- 2. Did not receive any disallowed medications or undergo any disallowed therapeutic procedures as described in Protocol Section 6.6.2:
 - Experimental interventions or therapies
 - Eculizumab or other agents that act on the complement pathway
 - Therapeutic plasma exchange/plasma infusion following randomization
- 3. Met inclusion criteria (IC) in the study:
 - IC 4: TMA within ≤ 14 days prior to Screening is associated with at least one of the following triggers:
 - a) Autoimmune (lupus nephritis or systemic sclerosis-associated TMA [SSc-TMA])
 - b) Infection
 - c) Solid organ transplant (eg, kidney, pancreas, liver, heart, or small bowel)
 - d) Drugs
 - e) Malignant hypertension

- IC 5: Confirmation of all of the following laboratory findings during the Screening Period and/or ≤ 14 days prior to the start of the Screening Period:
 - a) Platelet count $< 150,000/\mu$ L
 - b) $LDH \ge 1.5 \times upper limit of normal and hemoglobin \le LLN (based on age and sex)$
 - c) Acute kidney injury as defined by meeting 1 or more of the following criteria (for kidney transplant recipients, the pre-TMA value is based on post-transplant eGFR):
 - Acute decline in eGFR \geq 50% from pre-TMA value (the pre-TMA value must be \leq 12 months prior to Screening)
 - New acute kidney injury with an eGFR \leq 30 mL/min/1.73 m²
 - New initiation of dialysis due to TMA requiring > 1 session and for no more than 14 days prior to Screening
- 4. Did not violate important exclusion criteria (EC) in the study, including the following:
 - EC 1: Any known gene mutation that causes aHUS
 - EC 3: Known chronic kidney disease (CKD):
 - In participants with native kidneys: $eGFR \le 45 \text{ mL/min}/1.73 \text{ m}^2$ by the CKD-Epidemiology Collaboration (CKD-Epi) equation (Levey, 2009) due to any cause or ongoing acute kidney injury requiring dialysis treatment lasting for > 14 days prior to Screening.
 - In kidney transplant recipients: determination of the CKD threshold will be based on Investigator judgment.
 - EC 5: Primary and secondary glomerular diseases other than lupus

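### SAP Table 2 counts LDH up to 1.5 × ULN as normalized, so Complete TMA Response and hematologic response can be credited with LDH above normal

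*SAP*

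**What the plan says.** Protocol Section 3.2.1 has Complete TMA Response "defined as the normalization of hematologic parameters (platelet count and LDH", and adds an eGFR improvement of at least 30%. Protocol Section 3.2.2 asks for normalization of the same two blood parameters for hematologic response. Neither section, nor Protocol Table 5, puts a number on normal LDH.

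SAP Section 5.1, Table 2 does. The row reads "Normalization of LDH (defined as LDH" and is completed on the next line as at most "1.5 × upper limit of normal". The platelet row sets normalization at 150,000/µL or more, without transfusion support in the previous 7 days. All three parameters must be met together and confirmed at least 24 hours apart.

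At entry, Protocol Section 5.1, criterion 5b requires LDH of at least 1.5 × ULN, and SAP Section 6.3 repeats this for the Per-Protocol Set. The window is wide: "Confirmation of all of the following laboratory findings during the Screening Period and/or" up to 14 days before it.

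For safety summaries, SAP Section 7.7.3.1 sorts laboratory results as low, normal or high against the normal range. LDH is in the clinical chemistry panel (Protocol Table 9).

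SAP Section 4.2, "Changes from Analyses Specified in the Protocol", does not mention the LDH cut-off, and neither does the version table in SAP Section 4.3.

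**The concern.** A component labelled as normalization is satisfied by values up to 50% above the upper limit of normal. An LDH of 1.3 × ULN would be high in the shift tables and normalized in the primary endpoint of the same report.

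The cut-off also coincides with the entry limit, so a participant who entered just above 1.5 × ULN needs only a small fall to satisfy this component. Because the qualifying LDH may predate Day 1 by up to 28 days (14 before Screening plus 14 of Screening), a participant may already satisfy it at baseline.

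The definition reaches further than the primary endpoint. It carries into hematologic response at Week 26 and at every visit, time to response, Loss of TMA Response and Complete TMA Response at Week 52. For Loss of TMA Response, an LDH that rises from normal to 1.4 × ULN would not count as a failed component. What is at stake is what a reported complete or hematologic response means, in a study whose remaining efficacy output is descriptive response rates with confidence intervals.

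**Working it through.** **The plan's own figure.** The only published calculation on this endpoint is the sample size (Protocol Section 9.2, SAP Section 9.2): two-sided Fisher's exact test at 0.05, 35% versus 70%, 50 per group, 10% dropout, about 90% power.

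- Evaluable per group: 50 × (1 − 0.10) = 45.
- Power = sum of Bin(x; 45, 0.35) × Bin(y; 45, 0.70) over all (x, y) with Fisher p ≤ 0.05 = 88.3%.

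This agrees with the stated figure. It does not settle the LDH question, because neither document says which LDH limit the 35% and 70% assume. Power or response rates under another cut-off cannot be derived.

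**The cut-offs side by side.** Write L = LDH / ULN.

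| Parameter | Entry | Response | Overlap |
|---|---|---|---|
| LDH | L ≥ 1.5 | L ≤ 1.5 | L = 1.5 |
| Platelets (/µL) | < 150,000 | ≥ 150,000 | none |

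Not above normal, as the shift tables use the term, is L ≤ 1.0. The band 1.0 < L ≤ 1.5 is therefore high in SAP Section 7.7.3.1 and normalized in Table 2.

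**Direction.** Any pair of assessments (with any value in between) that has L ≤ 1.0 throughout also has L ≤ 1.5 throughout. Every responder at ≤ ULN is thus a responder at ≤ 1.5 × ULN, no later in time. With the same participants in the denominator, the rate at ≤ 1.5 × ULN is at least the rate at ≤ ULN. This does not extend to Loss of TMA Response or Complete TMA Response at Week 52, because their denominators are the responders themselves and change with the cut-off.

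**Who changes category.** For Complete TMA Response a participant must:

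1. meet the platelet and eGFR criteria together with confirmed L ≤ 1.5 at some time in the 26 weeks; and
2. at no time in that period meet them together with confirmed L ≤ 1.0.

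A participant who passes through the 1.0 to 1.5 band and later reaches L ≤ 1.0 with the other criteria met is a responder either way. A participant in the band who fails platelets or eGFR is a nonresponder either way. No LDH distribution is given, so the count is unknown and may be zero.

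**Weight of one participant.** SAP Section 4 gives 16 enrolled, and allocation was 1:1. Arm sizes are not stated, so 16 / 2 = 8 per arm is an assumption.

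- 1/8 = 12.5 percentage points.
- If the split were 7 and 9: 1/7 = 14.3 and 1/9 = 11.1 points.

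The mITT Set may be smaller than 16, which would make each step larger.

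**The case against.** The strongest reply is that the protocol gives no LDH number and leaves methods to be elaborated in the SAP (Protocol Section 9.4), so the SAP fills a gap and contradicts no figure. That stands. A reader might infer that the SAP loosened a stated protocol limit, or did so after the decision to terminate. The documents show neither. There was no limit to loosen, and the version table records no LDH change between SAP versions, although that does not prove when the cut-off was set. What remains is that filling in normalization should keep the meaning of the word, or say openly that it does not.

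Second, reversing the entry criterion is the pattern for platelets too, and the platelet cut-off is equally absent from Section 4.2. This is fair, and it weakens any argument from the shared threshold alone. But the platelet rows do not overlap, whereas the LDH rows do, and the LDH cut-off takes in values above the reference range.

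Third, LDH change from baseline and the shift tables will show persistent elevation. They will, but neither summary is tied to responder status, so they do not show how many responses rest on a raised LDH.

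Fourth, SAP Section 4.2 drops all hypothesis testing and treatment comparison, and the same cut-off applies to both arms. This is correct: type I error is not at issue, and nothing in the documents shows bias between arms.

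**Conclusion.** The point holds as a mismatch between label and definition that the SAP neither explains nor discloses. As written, the SAP can report LDH above normal as normalized in the primary, hematologic, time-to-response and loss-of-response endpoints.

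The direction is certain for the response rates: raised or unchanged. The size is not known. The figure of 12.5 points is the weight of one participant under an assumed 8 per arm, not an estimate of the effect.

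A reader might infer that everyone with confirmed LDH between 1.0 and 1.5 × ULN is turned from nonresponder to responder. The documents do not support this, because platelets and eGFR must also be met and confirmed, and response may occur at any time in 26 weeks. Nor do they require the present cut-off to be withdrawn. The protocol sets no number, and replacing the primary definition in a study already being terminated would itself be a late endpoint change. Reporting both cut-offs is enough.

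**What to change.** - Report Complete TMA Response and hematologic response with LDH ≤ ULN alongside the ≤ 1.5 × ULN version. Use the ULN of the reporting laboratory, since the confirming value may be central or local.
- Give the 1.5 × ULN component a label that describes it, in place of normalization, and state its rationale.
- List it in SAP Section 4.2 as the SAP's reading of a protocol term that had no number.
- Use a strict inequality for response (LDH < 1.5 × ULN) so that no value meets both entry and response.

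The data are already collected, and the shift tables already need the normal ranges. The cost is SAP wording and one extra table. The response rate at ≤ ULN may be lower than the one now planned.

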5.2. Secondary Endpoints

The following is a list of secondary efficacy endpoints. Due to early termination of the study, there are no longer any "key secondary endpoints" with multiplicity adjustment.

- 1. Time to complete TMA response (measured in days from Day 1 to the first day that the participant satisfies the criteria for complete TMA response) during the 26-week randomized Treatment Period.
 - TMA response occurs on the first day when all components of TMA response are met simultaneously, with each component meeting the requirement at 2 separate assessments obtained at least 24 hours apart, and any measurement in between.
- 2. Achievement of hematologic response at Week 26.
- 3. Change from Baseline in eGFR at Week 26.
- 4. On dialysis at Week 26.
- 5. Time to response for each TMA parameter (Table 2) during the 26-week randomized Treatment Period
 - Hematologic response
 - Renal response
- 6. Achievement of individual component of complete TMA response at all scheduled assessments
 - Hematologic response
 - Renal response
 - At least one of the TMA parameters
- 7. Changes from Baseline in hematologic response parameters at all scheduled assessments
 - Platelets
 - LDH
 - Hemoglobin
- 8. Increase in hemoglobin at Week 26 of
 - $\geq 2 \text{ g/dL}$
 - $\geq 1 \text{ g/dL}$
- 9. Change in kidney function
 - Change from Baseline in eGFR at all scheduled assessments
 - Change from Baseline in dialysis requirement at Week 26 and Week 52
 - Duration of dialysis (for participants who had dialysis within the 26-week randomized Treatment Period or within the study)

- 10. Complete TMA response at Week 52 among participants who achieved complete TMA response during the 26-week randomized Treatment Period
- 11. Loss of TMA response during the 26-week randomized Treatment Period (for participants who achieved complete TMA response during the 26-week randomized Treatment Period)
- 12. TMA relapse during the Post-Treatment Follow-up Period (for participants who achieved complete TMA response during the 26-week randomized Treatment Period)
- 13. Change in patient-reported outcomes as measured by Functional Assessment of Chronic Illness Therapy-Fatigue (FACIT-Fatigue) at all scheduled assessments

5.3. Exploratory Endpoints

The exploratory endpoints of the study are as follows:

- Exploratory biomarkers will be assessed in blood and urine for change from Baseline and may include, but are not limited to, markers of vascular damage, renal injury, and complement dysregulation (eg, soluble terminal complement complex, factor Ba). Exploratory biomarker assessments will be detailed in a separate, exploratory biomarker SAP.
- Change in patient-reported outcomes as measured by EuroQol 5-Dimension 5-Level (EQ-5D-5L) and Kidney Disease Quality of Life instrument[™]-36 items (KDQOL-36) at scheduled visits
- 3. Incidence of complement dysregulation-related mutations
- 4. Health resource utilization by Week 26 and Week 52 including:
 - Number, underlying reason, and duration of hospitalizations (including stays in intensive care unit, if applicable)
 - Number of outpatient medical encounters (including physician or emergency room visits)
- 5. Overall survival by Week 26 and Week 52

5.4. Pharmacokinetic and Pharmacodynamic Endpoints

The pharmacokinetic (PK) endpoints of the study are as follows:

- 1. Serum concentrations of ravulizumab over time
- 2. Serum free complement component 5 (C5) concentrations (absolute value, change from Baseline, and percentage change from Baseline) over time
- 3. Serum total C5 concentrations (absolute value, change from Baseline, and percentage change from Baseline) over time
- 4. Incidence of antidrug antibodies (ADAs) and assessment of immunogenicity

5.5. Safety Endpoints

The safety and tolerability endpoints of the study are as follows:

- 1. Incidence of adverse events (AEs) and serious adverse events (SAEs) by Week 26 and Week 52
- 2. Incidence of major adverse cardiovascular events (MACEs) by Week 26 and Week 52
- 3. Changes from Baseline in vital signs and laboratory parameters at scheduled assessments

5.5.1. Adverse Events

AEs are defined in Protocol Section 10.3.

MACEs as determined by the Investigator will be assessed as part of the planned evaluation of AEs. A MACE is defined as any of the following:

- Nonfatal myocardial infarction
- Nonfatal stroke
- Death from cardiovascular disease

Adverse events of special interest (AESIs) include meningococcal infections as defined in PA2 Section 8.4.6.

5.5.2. Vital Signs

Vital signs are systolic and diastolic blood pressure [mm Hg], heart rate (beats per minute), respiratory rate (breaths per minute), body temperature (degrees Celsius [°C] or degrees Fahrenheit [°F]), and pulse oximetry (%).

5.5.3. Laboratory Assessments

Laboratory assessments are defined in Protocol Section 10.2, where the laboratory tests as detailed will be performed by the central laboratory or designated ancillary laboratories. Local laboratory results are only required in the event that the central laboratory results were not available in time for either study drug administration and/or response evaluation. In the event of duplicate samples from local and central laboratories (for any time point), central laboratory results will be used for analysis.

5.5.4. Electrocardiograms

A single 12-lead electrocardiogram (ECG) will be conducted according to the schedule of activities (SoA) in the protocol to obtain heart rate, PR, QRS, QT, and corrected QT (QTc) intervals. The QT interval will be corrected for heart rate using Fridericia's formula (QTcF).

5.5.5. Physical Examination

A complete physical examination will include, at a minimum, assessments of the following organs/body systems: skin, head, ears, eyes, nose, throat, neck, lymph nodes, chest, heart, abdomen, extremities, musculoskeletal, and neurological state. An abbreviated physical

examination will include, at a minimum, a body-system relevant examination based on Investigator judgment and participant symptoms.

5.5.6. Immunogenicity

Blood samples will be collected to test for the presence of ADAs to ravulizumab in serum according to the SoA in the protocol. Samples with confirmed positive ADA will further be tested for ADA titer and the presence of neutralizing antibodies.

